Quality Assurance and Quality Control.....	37
12 Publication Policy	37
13 Literature References	38
14 Appendix A: Grading of Severity for Adverse Events	39

15	Appendix B: Flu-Pro – Participant Reported Tool	44
16	Appendix C: Modified Jackson Score – Investigator Assessment Tool.....	48
17	Appendix D: Schedule of Events	49

LIST OF ABBREVIATIONS

ABTC	Advanced Bioaerosol Technology Core
ACGIH	American Conference of Governmental Industrial Hygienists
ACH	Air changes per hour
ADCC	Antibody-dependent cellular cytotoxicity
ALC	Absolute lymphocyte count
ALT	Alanine transaminase
BAMA	Binding antibody multiplex assay
BP	Blood pressure
CBC	Clinical & Biostatistics Core
CFR	Code of Federal Regulations
CHIVITT	Controlled human influenza virus infection transmission trial
COPD	Chronic obstructive pulmonary disease
Cr	Creatinine
CR	Control Recipient
CRF	Case Report Form
DMID	Division of Microbiology and Infectious Diseases, NIAID, NIH, DHHS
DSMB	Data and Safety Monitoring Board
ELLA	Enzyme-linked lectin assay
EMIT	Evaluating Modes of Influenza Transmission
FOCBP	Female of childbearing potential
FRNT	Focus Reduction Neutralization Test
GBS	Guillain-Barré Syndrome
GCP	Good Clinical Practice
GMP	Good Manufacturing Practice
HA	Hemagglutinin
HAI	Hemagglutination inhibition
Hgb	Hemoglobin
HR	Heart rate
ICF	Informed Consent Form
ICH	International Council on Harmonisation
iEBA	Infectious exhaled breath aerosols
IR	Intervention Recipient
IV	Intravenous
IRB	Institutional Review Board
MN	Microneutralization
MOP	Manual of Procedures
NA	Neuraminidase
N	Number (typically refers to subjects)
NIAID	National Institute of Allergy and Infectious Diseases, NIH, DHHS
NIOSH	National Institute for Occupational Health and Safety, CDC, DHHS
NIH	National Institutes of Health
NSAID	Non-steroidal anti-inflammatory drug
PHI	Protected health information
PI	Principal Investigator
PLT	Platelets
PPE	Personal protective equipment

PPM	Particles per minute
RR	Respiratory Rate
SAB	Scientific Advisory Board
SAR	Secondary Attack Rate
SOP	Standard Operating Procedure
SpO ₂	Oxygen saturation
WBC	White blood cells
WHO	World Health Organization
UHC	University Health Center (College Park)
UMB	University of Maryland, Baltimore
UMD or UMCP	University of Maryland, College Park
UMIC	UMaryland Immediate Care (Baltimore, MD)
UMMC	University of Maryland Medical Center (Baltimore, MD)
UV	Ultraviolet light

PROTOCOL SUMMARY

Title: Evaluating Modes of Influenza Transmission through the conduct of controlled human influenza virus infection transmission trials (CHIVITTs)

Population: up to 200 persons, among which 175 may be Recipients aged 18 through 49 and 25 may be Donors aged 18 through 59 years

Number of Sites: at least 2 (University of Maryland, Baltimore and University of Maryland, College Park)

Study Duration: approximately 5 years

Subject Duration: Up to approximately 2 months.

Primary Objective:

- The primary objective of EMIT-2 is to use a randomized controlled trial (RCT) design to implement interventions which are known to reduce inhalation (airborne) transmission, so that the contribution of transmission by route of aerosols for influenza may be identified.

Primary Endpoint:

- Secondary attack rate (SAR) of influenza in Recipients participating in RCTs of air sanitation-ventilation-filtration and contact-fomite interventions, so called controlled human influenza virus infection transmission trials (CHIVITTs).

Secondary Objectives:

- To measure influenza viral parameters in both Donors and Recipients, including the incidence, duration, and quantity of virus shedding
- To measure influenza illness parameters in both Donors and Recipients, in order to assess the impact of aerosol exposure to influenza virus on disease severity
- To evaluate the role of serologic and mucosal antibody levels on influenza transmission, susceptibility, and immunologic response to infection
- To estimate the infective dose of influenza via aerosol inhalation, through measurement and modeling of aerosol size, virus number per aerosol particle, deposition and environmental dispersion characteristics, and rate of shedding

2 BACKGROUND INFORMATION AND SCIENTIFIC RATIONALE

[figure not shown]
2.1 Background Information

Influenza has a high disease burden to the United States and globally. However, fundamental aspects of influenza virus epidemiology remain poorly understood. Determination of the relative importance of droplet nuclei and droplet sprays in influenza transmission is relevant to the control of both seasonal and pandemic influenza. It will largely settle the debate about the most appropriate personal protective equipment for healthcare workers (respirators or surgical face masks) and pave the way for the development of interventions or control measures specific to the dominant mode of transmission. Although typical modes of influenza transmission between humans may include aerosol, large respiratory droplet, and contact^{1,2}, the relative importance among these three routes is still under debate.¹ The importance of this question is emphasized in the NIAID strategic plan for a universal influenza vaccine,³ which identifies as a “key unanswered question the relative contribution of aerosols, droplets, and fomites as modes of transmission.”

To answer this critical question the CDC funded a project called “Evaluating Modes of Influenza Transmission using a Human Challenge Model” (hence forth referred to as EMIT-1; PIs: [name], [name], and [name]). EMIT-1 was designed as an experimental study of human-human transmission from volunteers deliberately infected with Good Manufacturing Practices (GMP) well-characterized lab-grown influenza viruses. In EMIT-1, “donors” were nasally inoculated with a GMP A/H3N2 virus and susceptible volunteers (“recipients”) were exposed to the donors through prescribed close living conditions. EMIT-1 failed to achieve the planned attack rate of influenza transmission, and this was largely hypothesized to be a result of the lack of significant illness and low numbers of shedding of influenza virus with infection.⁴ In the wake of EMIT-1, a two-day international workshop “Influenza Transmission and the Built Environment: Understanding Modes of Transmission in a Sustainable Future” was held in March 2014 to review the results and chart a path forward. Workshop attendees proposed an alternative approach for studying the relative contribution of the various modes of influenza transmission and recommended to abandon inoculation with GMP viruses in favor of donors who are naturally infected cases, which could be recruited from a medical clinic.

[figure not shown]
NIAID-funded project “Evaluating Modes of Influenza Transmission using Innovative Technologies and Design in Controlled Environments” (hence forth referred to as EMIT-2; PD: [name]) is in response to NIAID funding opportunity “Multidisciplinary Studies to Improve Understanding of Influenza Transmission” (RFA-AI-20-08). EMIT-2 will perform a series of controlled clinical studies of influenza transmission to comprehensively evaluate viral, host, physical, and environmental factors that facilitate efficient human-to-human influenza transmission. In these studies, healthy participants who are deemed to be susceptible to influenza (recipients) will be in contact with participants naturally infected with influenza virus (donors). These transmission studies are hence forth referred to as controlled human influenza virus infection transmission trial (CHIVITT) studies.

This document represents the EMIT-2 CHIVITT Protocol. The EMIT-2 Donor portion of this document is for the enrollment of persons naturally infected with influenza who will participate in a CHIVITT. Under the CHIVITT Protocol portion of this document, EMIT-2 Recipients (who have already been screened under the EMIT-2 Recipient Protocol, UMB IRB HP-97730) will consent to be “exposed” to influenza from infected Donors. The EMIT-2 Donor enrollment and CHIVITT activities will be conducted during the winter (during the natural annual influenza season) of each designated year.

2.2 High-Level Overview of EMIT-2 Program

[figure not shown]
The NIH U19-funded EMIT-2 program is made up of 2 research Projects and 2 scientific Cores. Research **Project 1** consists of the randomized controlled trials which will determine the dominant mode of transmission, the impact of aerosol exposure on disease severity, and the contribution of serological and mucosal susceptibility on infection. Research **Project 2** consists of developing and applying analytical models of transmission, with comparisons to ferret transmission studies. The **Clinical and Biostatistics Core** is responsible for providing the clinical infrastructure, trained personnel, regulatory compliance, quality management, and clinical oversight necessary to conduct the CHIVITT studies. The **Advanced Bioaerosol Technology Core** will be developing and evaluating a novel compact ambient (environmental) sampling and culture device, a next-generation infectious exhaled breath aerosols (iEBA) sampler, an optimized virus collection and cell culture line, and a digital culture microarray. These four components will synergistically be working collaboratively together to achieve the goals of the EMIT-2 program. The hypothesis is that infectious aerosols are a major contributor to influenza transmission and that ventilation, air hygiene, and reduction of aerosol exposure will be associated with a reduction in both secondary influenza attack rates and disease severity.

2.3 Scientific Rationale

The overarching objective of the EMIT-2 program is to evaluate how viral aerosol shedding and ventilation interact to facilitate human-to-human influenza transmission and provide insights into correlates of protection in the setting of absent or low hemagglutination inhibiting (HAI) antibodies using a controlled environment. The central hypothesis of EMIT-2 is that inhalation of infectious aerosols (small size infectious particles suspended in air) is the dominant mode of influenza transmission. EMIT-2 will carefully characterize and quantify exhaled infectious aerosols and the indoor environment while assessing the relative effect of planned interventions. For example, in one planned transmission experiment, under conditions with low ventilation and low air hygiene, half of the cohort of recipients will don face shields and use hand sanitizer every 15 minutes while the remaining half of recipients will not don protection or make frequent use of hand sanitizer; all recipients will be instructed to engage in prescribed close-contact activities (e.g., play a board game for 2 hours) with donors who are infected with influenza. As a result, a secondary attack rate of influenza transmissions of approximately 25% is intended to occur under low air-hygiene conditions with a cumulative total of up to 60 hours of exposure of each recipient. The duration of exposure is chosen to match that used in previous trials (Killingley B et al., *J. Infect. Dis.* 2012;205:35–43 and Nguyen-Van-Tam JS et al., *PLoS Pathog.* 2020;16:e1008704).^{4,5} Over the course of approximately 5 influenza seasons, a number of controlled transmission experiments are to be conducted with variable air hygiene conditions. The scientific and engineering technologies and aims of the EMIT-2 program are

contingent upon successfully facilitating secondary influenza infections, i.e., influenza transmissions from index cases (Donors) to exposed contacts (Recipients).

2.3.1 EMIT-2 Recipients

The EMIT-2 Recipient Protocol (UMB IRB HP-97730) is a continuous (yearlong with a duration of ~5 years) screening protocol to identify healthy “susceptible” adults, based on lack of potentially protective antibody, to serve as the recipient pool for exposed contacts in CHIVITT. Persons who have consented to the EMIT-2 Recipient Protocol have agreed to be contacted during the winter seasons for whether they would agree to participate in a CHIVITT. Formal separate consent will be performed for recipients that agree to participate in a CHIVITT.

2.3.2 EMIT-2 Donors

This protocol will describe the EMIT-2 Donor recruitment process for the enrollment of persons naturally infected with influenza index cases who agree to participate in a CHIVITT. The recruitment process will be performed from among the community, beginning with case identification on the campuses of the University of Maryland, Baltimore (UMB) in association with the University of Maryland Medical Center (UMMC) and the University of Maryland, College Park (UMCP). From these 2 campuses, investigators may also add additional sites to potentially recruit influenza index cases, including health centers on college and university campuses in the Baltimore area, the Johns Hopkins Medical Institutions emergency and outpatient departments and other local urgent care centers or local primary care practices. Each participating site must have IRB approval.

2.4 CHIVITT

This protocol will describe the general conduct of the CHIVITT, wherein we will estimate the relative contribution of aerosol inhalation (airborne), spray deposition (large droplet), and touch (contact-fomite) transmission on the spread of influenza, by determining the secondary attack rate (SAR) of influenza among uninfected volunteers (Recipients) who closely interact with naturally influenza-infected index

cases (Donors). The close interactions are designed to mimic real-world potential exposures to influenza. To identify the dominant mode of transmission, various interventions will be employed. The exposure room environment can be tuned to a low ventilation minimal filtration environment or a high ventilation, filtration, and air disinfection environment. The residential and common room environment may be supplemented with in-room air filtration and/or germicidal UV air disinfection to achieve high air hygiene conditions to block inhalation of infectious aerosols. Transmission via spray deposition may be blocked by face shield interventions. Touch (contact-fomite) transmission may be blocked through strict hand hygiene and surface cleaning protocols. Aerosol inhalation transmission may be further reduced by the donning of face masks. The determination of SAR in Recipients will be performed through a standardized procedure of collected respiratory specimens and daily symptom surveys. The monitoring and management of influenza illness will be conducted to ensure the welfare of all study participants.

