5 CHIVITT OBJECTIVES

Table: Objectives and Endpoints (Outcome Measures)

Objectives	Endpoints (Outcome Measures)
Primary	

 • To determine the relative contribution of the various modes of transmission 	
 • SAR of influenza infection will be determined through virological confirmation, symptomatic infection, or serological evidence
Secondary	

 • To measure influenza viral parameters in Donors and Recipients • To measure influenza illness parameters in Donors and Recipients to assess the impact of aerosol exposure to influenza on disease severity • To evaluate the role of serologic antibody levels on influenza transmission, susceptibility, and immunologic response to infection 	
 • Incidence, duration, and quantity of virus shedding in donors and recipients • Disease severity parameters in donors and recipients • HAI, NI, and FRNT titers, HA/NA anti-stalk ELISA, and ADCC reporter assays. • Measurement and modeling of aerosol size, virus number per aerosol particle,

• To estimate the infective dose of influenza virus	deposition and environmental dispersion characteristics, and rate of shedding
Exploratory	

 To evaluate the role of mucosal antibody and cellular immunity in transmission and susceptibility. To characterize the quantum of airborne influenza infection and extend models of aerosol inhalation risk from well-mixed to non-well mixed conditions and the personal breathing zone. 	
 Potential assays include IgA in nasal secretions and collection and analysis of cellular immune markers. Exhaled breath viral loads and ambient viral concentrations, environmental parameters, video analysis of individual movement and interpersonal proximity and behaviors.

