6.1 General Outline of Activities During Each CHIVITT Cohort

The CHIVITT is to be conducted as a randomized, open, controlled study. Recipient participants for each cohort will enter the study hotel quarantine facility and be housed in individual hotel rooms. After a two-day run-in period to ensure that Recipients are free of preexisting respiratory infections *Exposure Events* will be held in a specially prepared event room.

Recipient participants of each cohort will be randomized to an intervention group or no intervention (Control Recipients, CR). Before entering their first *Exposure Event* each Intervention Recipients (IR) will be trained on how to comply with the intervention. IRs will be required to wear a lightweight plastic face shield, comply with hand hygiene (i.e., using a hand sanitization product every 15 minutes, plus periodic hand washing with soap and water), and avoid face touching during each planned *exposure event*. The face shield may only be removed after leaving the exposure room to go to the bathroom, for other short comfort breaks, and at mealtimes. In these instances, hand hygiene will be used after removing or replacing the face shield; and Donors will not be present. Hand washing with soap and water will be required before meals. IR will be separated from Donors by more than 6 feet during meals. The exposure room will be supervised by a trained member of the study staff who will monitor to ensure that Intervention Recipients wear the face shield continuously, are separated from Donors at meals, and do not touch their faces. Small sticks (e.g., coffee stirrers) will be provided to allow IRs to scratch their faces.

Exposure events are to occur as controlled (prescribed) activities within the exposure room. Exposure events will extend for up to 15 hours per day when Donors are available and able to participate (e.g., 15 hours 8am to 11pm). Each Recipient will participate in up to 60 hours of *Exposure Events* (e.g., 4 days at 15 hours/day) which may be spread over up to 9 or 10 days. During each *Exposure Event* multiple 1-3 hour group activities will be planned and supervised by trained members of the study staff. The group activities are intended to be entertaining and may consist of participating in a card game, board game, foosball game, karaoke, or other group activity which facilitates crowding, loud talking, etc. for potential influenza transmission.

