8.1.2 Exposure Events

- Exposure events will be held in a large hotel room each lasting up to several hours. Each cohort will experience multiple exposure events over the course of their stay. Each exposure event will be either a high or low air hygiene exposure.
- Low air hygiene conditions will be limited by the quarantine hotel's standard mechanical ventilation (~0.7 air changes per hour) and may be further limited by sealing windows and or blocking bathroom exhaust fans and hallway supply as necessary to control carbon dioxide levels to simulate a poorly ventilated public space while remaining within the OSHA permissible exposure limit.
- High air hygiene conditions will supplement the building's mechanical ventilation with portable HEPA filter units and / or germicidal ultraviolet air disinfection (either upper-room 254 nm or direct 222 nm UV-C or similar technologies and wavelengths with monitoring to confirm compliance with current ACGIH Threshold Limit Values).
- The room in which the exposure events occur will have the ventilation rate, CO₂ concentration, temperature, and relative humidity continuously monitored and supplemental heating, cooling, and dehumidification will be supplied to maintain comfort (~20°C ± 3) and relative humidity <40%.
- Recipients will be randomized to spray-borne and touch transmission intervention (Intervention Recipients, IR) and control (Control Recipients, CR) within each exposure event, except that the initial exposure event may include only CR to assess the SAR and power of the study design for the remaining events.
- Prescribed group activities will be planned by the study team to involve close-distance interactions between study participants (donors and recipients). Due to the unpredictability of when donors may become available, it is intended to be flexible for the scheduling of these events for the time of day, duration, and frequency of number of days. For example, donors and recipients will engage in supervised playing of board games, watching films, eating meals together while ensuring that randomized designated IR individuals comply with spray-borne and touch transmission prevention interventions (face shield use, hand sanitization, and no-touch-face rules). Outside of the exposure events, donors and recipients are to be housed in separate rooms to prevent inadvertent "contamination" or transmissions outside of the prescribed group activities.

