9.2 Sample Size Considerations

We estimate effect sizes of interest based on an expected SAR of 25% and two alternate hypotheses that: a) long-range aerosol transmission accounts for 75% of transmission and b) contact, fomite, and spray-borne transmission account for 60% transmission. These hypotheses are essentially attributable fractions, not the expected effect size of the interventions. The interventions, unfortunately, cannot cleanly block one mode without impacting transmission via other modes. Therefore, we derived the estimated effect sizes for the interventions by analysis of planned interventions and their impact on each mode of transmission. It is assumed that hand hygiene and face shield is 100% effective for contact and spray-borne transmission and the effectiveness for short-range aerosols is based on the work of Lindsley⁵ and Bischoff⁶. The air hygiene (ventilation, filtration, and germicidal UV light) intervention will be designed to be 100% effective against long-range aerosol transmission using a validated computational model of these systems, to be developed by Research Project 2 of the EMIT-2 U19 Project, to achieve the equivalent of > 60 ACH. However, air hygiene interventions are relatively less effective against short-range aerosol transmission.

Because of incomplete blockage of aerosol transmission by air sanitation and partial blockage of short-range transmission by the face shields, we assume marginal effect size of 79% reduction in the observed SAR. To compute power, we use one-sided alternatives because we do not expect that either intervention is capable of increasing transmission. Given a sample size of 54 in an intervention group, we will have 84% power to detect the intervention effect with an alpha level of 5%.

For power to detect an effect of contact, fomite, and spray-borne transmission, we assume a marginal effect size of 76% reduction in observed SAR. Given a sample size of 63 in an intervention group, we will have 84% power to reject the null hypothesis of no effect with the hand hygiene and face shield.

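### Section 2.4 promises separate shares for inhalation, spray and touch, but shield and hand hygiene are only ever given together, so attack rates cannot separate spray from touch

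*Protocol*

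**What the plan says.** **The promise.** Section 2.4: "we will estimate the relative contribution of aerosol inhalation (airborne), spray deposition (large droplet), and touch (contact-fomite) transmission on the spread of influenza". The same sentence gives the means: "by determining the secondary attack rate (SAR) of influenza among uninfected volunteers (Recipients". In section 5 the primary objective is "To determine the relative contribution of the various modes of transmission", with the SAR as its endpoint. The Protocol Summary is narrower. There the interventions are applied "so that the contribution of transmission by route of aerosols for influenza may be identified".

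**The design.** Section 6.1 has two randomised groups: "Recipient participants of each cohort will be randomized to an intervention group or no intervention (Control Recipients, CR". Of the intervention group it says "IRs will be required to wear a lightweight plastic face shield, comply with hand hygiene", and it adds the ban on face touching. Section 8.1.2 describes the same pair: "Recipients will be randomized to spray-borne and touch transmission intervention (Intervention Recipients, IR) and control (Control Recipients, CR". The example experiment in section 2.3 gives shield and sanitiser to the same half of the cohort. The second factor is high versus low air hygiene, alternated within cohorts after Year 1 (section 6.1).

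**The overlap.** Section 9.2 treats contact, fomite and spray as one 60% fraction with one effect size. It says that the interventions cannot each act on one route alone, and it derives its effect sizes "Because of incomplete blockage of aerosol transmission by air sanitation and partial blockage of short-range transmission by the face shields".

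**The concern.** Section 2.4 names three routes and links the shield to spray and hand hygiene to touch, but no section defines a group that receives one without the other. It also mentions face masks, and no section makes them an arm. Two intervention effects cannot yield three route shares.

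The package is also not specific to spray and touch. Because the shield catches some short-range aerosol, the fall in SAR from Control to Intervention Recipients credits part of inhalation to the other routes if it is read as a share. That error would run against the trial's central hypothesis that inhalation dominates (section 2.3). At stake is what the final report can claim under the primary objective.

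**Working it through.** **Inputs (section 9.2 unless noted).** Control SAR 25%. Contact, fomite and spray share 60%, paired with a 76% SAR reduction. Long-range aerosol share 75%, paired with a 79% reduction. Package 100% effective on contact and spray. Air hygiene 100% effective on long-range aerosol. Shield partly effective on short-range aerosol, with no figure given. Arms from sections 6.1 and 8.1.2.

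**The plan's own contrasts.** The package takes the SAR from 25% to 25% × (1 − 0.76) = 6%; air hygiene takes it to 25% × (1 − 0.79) = 5.25%. Section 9.2 states 84% power for each. Assuming equal groups (the comparator size is not given), a pooled two-sample test at two-sided 5% gives 82.7% (n = 54) and 84.7% (n = 63); at the stated one-sided 5% it gives 89.8% and 91.1%. Either way these are powers for two contrasts, and neither separates spray from touch.

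**Step 1: can the cells separate the routes?** Work with hazards, −log(1 − SAR), which add across routes. Let L = long-range aerosol, S = short-range aerosol, D = spray, T = touch, p = fraction of S blocked by the shield and q = fraction of S blocked by high air hygiene.

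- Control, low air hygiene: L + S + D + T
- Intervention, low: L + (1 − p)S
- Control, high: (1 − q)S + D + T
- Intervention, high: (1 − p)(1 − q)S

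D and T enter only as D + T. With p and q taken as known (30%/10% and 50%/20% tried), the four equations have rank 3 for four routes, and the direction that cannot be seen is exactly D − T. With the three routes of section 2.4 the rank is 2.

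**Step 2: illustration.** Total hazard −log(0.75) = 0.2877; illustrative p = 30%, q = 10%.

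| Split L/S/D/T (%) | Control low | Intervention low | Control high | Intervention high |
|---|---|---|---|---|
| 60/10/25/5 | 25.0% | 17.5% | 10.6% | 1.8% |
| 60/10/5/25 | 25.0% | 17.5% | 10.6% | 1.8% |
| 60/10/15/15 | 25.0% | 17.5% | 10.6% | 1.8% |

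Adding shield-only and hand-hygiene-only cells raises the rank to 4, still with p and q known. The bundling is therefore the cause.

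**Step 3: is the package contrast the spray-plus-touch share?** At low air hygiene the hazard removed is D + T + pS, not D + T. On section 9.2's figures, read simply, 76 − 60 = 16 points are aerosol stopped by the shield, which is 16/76 = 21% of the reduction. On the hazard scale the reduction is 1 − log(0.94)/log(0.75) = 1 − 0.0619/0.2877 = 78.5%, a gap of 18.5 points. Both are approximate, because section 9.2 calls its effect marginal and it may average over air hygiene.

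**Step 4: what a share needs.** With p and q unknown, the four equations carry five unknowns (L, S, D + T, p, q), so an efficacy must come from outside. Solving, D + T = (Control high − Intervention high) − Intervention high × p/(1 − p). For the Step 2 cells, as shares of the total hazard, Control high is 0.39 and Intervention high is 0.063. This gives D + T = 32.0%, 30.0% or 26.4% for an assumed p of 0.1, 0.3 or 0.5.

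**The case against.** The best defence is that the protocol concedes much of this. Section 9.2 pools contact, fomite and spray, says the interventions overlap, and distinguishes attributable fractions from effect sizes. The Summary asks only for the aerosol contribution. Modelling, video and environmental sampling are planned, and a SAP may say how they will be used. This stands as far as it goes: nobody in the protocol reads the package contrast as a share, and modelling may help to apportion short-range aerosol. It does not rescue spray versus touch. Section 2.4 ties the estimate to the SAR, no section divides the two routes with the other data, and a SAP cannot create a contrast that the arms lack.

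Some stronger readings are tempting but unsupported:

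- *Section 5 and the Summary promise the three-way split.* Only section 2.4 names the three routes. Section 5 speaks of modes without listing them, and the Summary makes no such claim and needs no correction.
- *The two assumed reductions exceed 100% together, so the plan is incoherent.* They belong to alternate hypotheses. The shares, 75% and 60%, already sum to 135% and cannot hold in one scenario, so adding 79% and 76% shows nothing.
- *The Intervention/Control SAR ratio is a lower bound on the inhalation share, so a ratio above one half proves dominance.* Suppose p is near 0. An inhalation hazard share of 47% then gives (1 − 0.75^0.47)/0.25 = 0.506, so the raw ratio passes one half when inhalation does not. Sampling error matters too. With 63 per group, no clustering and SARs of 20% and 25%, the standard error of the log ratio is √(0.80/12.6 + 0.75/15.75) = 0.333, and the 95% lower limit of the ratio 0.80 is 0.80 × exp(−1.96 × 0.333) = 0.42.

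**Conclusion.** The point holds in a limited form. Section 2.4 states a property that the design lacks: spray and touch are completely aliased, whatever the sample size. This follows from the arms alone and needs no efficacy assumption beyond the package being given whole.

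Separately, the Intervention–Control contrast is spray plus touch plus part of inhalation. On section 9.2's figures it would exceed the contact and spray share by about 16 points (18.5 on the hazard scale). The direction follows from the protocol's own statement about shields; the size is approximate.

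The four-cell model flatters the plan. With air hygiene alternated within cohorts, the same Recipients may meet both conditions, and infections detected only by serology about a month later cannot be assigned to one of them.

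A reader might infer that the trial cannot address its hypothesis at all. The documents do not support that: the effects of air hygiene and of the package remain legitimate comparisons, and both bear on the Summary's aerosol objective.

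**What to change.** 1. Reword section 2.4 and the primary objective in section 5, in line with the Summary and section 9.2, so that the trial estimates two effects: air hygiene, and the combined shield and hand-hygiene package.
2. State that spray and touch will be reported only as one combined component.
3. Label any route share as model-based, conditional on stated efficacies of shield and air hygiene, with a sensitivity range.
4. If an Intervention/Control quantity under low air hygiene is reported, make it exploratory. Compute it as a ratio of −log(1 − SAR) with a confidence interval, state that it rests on the assumed 100% blockage of contact and spray, and restrict it to Recipients whose exposure was only under low air hygiene. Attach no dominance rule to its point estimate.

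The cost is wording, plus a short sensitivity analysis if shares are reported; no participants or arms are added. The protocol gives up a three-way claim that it cannot deliver. Keeping that claim would require separately randomised shield and hand-hygiene components with their own power, which is a larger trial.
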